2.3. PK Sampling Schedule

Blood (plasma) samples will be collected into K2EDTA tubes at the following time points: On Day 1 at 30 min before dosing, and 0.5 h (± 5 min), 1 h (± 5 min), 2 h (± 5 min), 3 h (± 10 min), 4 h (± 10 min), 6 h (± 10 min), 8 h (± 15 min), and 12 h (± 15 min) after dosing; on Day 2 at 24 h (± 2 h) and 36 h (± 2 h) after dosing; on Day 3 at 48 h (± 2 h) after dosing; and on Day 4 at 72 h (± 2 h) after dosing, or early termination.

2.4. Analytical Methods

Plasma concentrations of zoliflodacin will be determined using a validated HPLC-MS/MS method. The analysis will be performed by KCAS Bioanalytical Services. Details are included in the assay validation. For details of sample collection, processing, storage, transportation, and bioanalysis, see the protocol, MOP, and assay validation documents.

2.5. Collection of Pharmacodynamic or Clinical Endpoints

Not applicable.

3. PHARMACOKINETIC ANALYSIS METHODS

3.1. Analysis Population and Handling of Missing Time Points

All subjects who received the study drug and who have at least one measurable drug concentration post-dosing will be included in the PK analysis population. Additionally, there will be a PK analysis subset, which includes all subjects who completed the PK part of the trial without any protocol violations or deviations that would likely affect the PK results and who have evaluable plasma concentration data for zoliflodacin from which at least the C_{max} and T_{max} can be determined (peak concentration and at least one decreased concentration after the peak observed). Zoliflodacin concentrations will be listed and shown graphically as individual profiles for all subjects in the PK analysis population, but concentration summary statistics, mean PK profiles, and NCA will use the PK analysis subset only. All enrolled subjects excluded from the PK analysis population or the PK analysis subset will be described in the PK Report, including reason for exclusion.

Collection of plasma samples outside of the protocol defined time window for the time point will not result in exclusion of the sample result from NCA. If a sample is collected more than 10 min outside of the protocol defined time window, the sample result will be excluded from calculation of summary statistics for the respective time point, as well as from plots of mean concentration.

Values below the lower limit of quantification (LLOQ) will be referred to as below the quantification limit (BQL). BQL values that precede the first PK concentration above the LLOQ will be imputed as 0 for linear plots and for all calculations including NCA and summary statistics, but will be excluded from semi-logarithmic plots. All other BQL values will be treated as missing for all analyses.

Missing pre-dose PK samples will have concentrations imputed as 0 for analysis. All other missing PK sample concentrations will not be imputed for the NCA. A geometric mean (GM) of concentrations will be treated as missing for sets of data points containing an imputed 0 value due to a BQL value.

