11.4 Final Analysis Plan

The ICH/ FDA Guidance Document E9 (Statistical Principles for Clinical Trials) will be followed for all statistical content.¹⁶ For categorical data, summaries of frequencies and percentages will be presented. Summaries for continuous data will include minimum, median, mean, standard deviation, and maximum. Details of study analyses for safety and PK data and their presentation will be described in the Statistical Analysis Plan (SAP) and accompanying Tables, Listings and Figures (TLF) templates. The SAP will be prepared and finalized by the DCC prior to final data lock. Analyses included in the CSR will be performed by the DCC after final data lock. Any change from originally planned statistical analyses will be reported in the final clinical study report (CSR).

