3.3. Dosing and Pharmacokinetic Sampling Summary

Subject dose administration times will be presented (PK Listing 2). Cases that potentially affect the analysis will be discussed.

Protocol deviations related to dosing or PK sampling will be listed (PK Listing 3) and summarized in the PK Report text. Deviations to be included in the PK Report include:

- Treatment administration deviations
- Blood specimen not collected
- Plasma specimen result not obtained
- Specimen temperature excursion
- Required specimen collected out of window
- Subject vomiting within 24 h of dose

- Subject ingestion of prohibited food or within the prohibited window after dosing
- Any other deviation determined by the PK analyst to be potentially affect PK

Drug plasma concentrations will be listed by subject (PK Listing 4), with nominal and actual time associated with the sample indicated (nominal time is defined as the time in h since the start time of the dose). Both laboratory reported concentration values, and modified concentration values used for analysis (for instance, imputation of 0 for a BQL value at baseline) will be included, as separate columns, in the listing.

Plasma drug concentrations will also be summarized (PK Table 2) and plotted. PK Figure 1 and PK Figure 2 will plot all individual subject plasma PK profiles, as linear and semi-logarithmic plots, respectively. Subject ID for each individual profile in these figures will be shown in a legend. GM plots of zoliflodacin PK profiles will be shown in PK Figure 3. Semi-log mean plots of zoliflodacin PK profiles will be shown in PK Figure 4.

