6. APPENDICES

APPENDIX 1. LIST OF PROPOSED PK TABLES

LIST OF PK TABLES

PK Table 1: Summary of Demographic and Baseline Characteristics of Subjects Included in the PK Analysis Population.....	11
PK Table 2: Summary Statistics for Concentrations by Nominal Time	12
PK Table 3: Summary Statistics for PK Parameters	13

PK Table 1: Summary of Demographic and Baseline Characteristics of Subjects Included in the PK Analysis Population

Parameter	PK Analysis Population (N=X)
Sex – N (%)	
Male	
Female	
Age (years)	
Mean (SD)	
Median	
Min, Max	
Height (cm)	
Mean (SD)	
Median	
Min, Max	
Weight (kg)	
Mean (SD)	
Median	
Min, Max	
BMI (kg/m²)	
Mean (SD)	
Median	
Min, Max	
Race – N (%)	
American Indian or Alaska Native	
Asian	
Black or African American	
Native Hawaiian or other Pacific Islander	
White	

PK Table 2: Summary Statistics for Concentrations by Nominal Time

Subject ID	Zoliflodacin Concentration (ng/mL) by Nominal Time ¹ After Dose (h)												
	0	0.5	1	2	3	4	6	8	12	24	36	48	72
99ZZZ001	x	x	x	x	x	x	x	x	x	x	x	x	x
99ZZZ002	x	x	x	x	x	x	x	x	x	x	x	x	x
99ZZZ003	x	x	x	x	x	x	x	x	x	x	x	x	x
...	x	x	x	x	x	x	x	x	x	x	x	x	x
Statistics													
N²	x	x	x	x	x	x	x	x	x	x	x	x	x
Mean	x.x	x.x	x.x	x.x	x.x	x.x	x.x	x.x	x.x	x.x	x.x	x.x	x.x
SD	x.x	x.x	x.x	x.x	x.x	x.x	x.x	x.x	x.x	x.x	x.x	x.x	x.x
GM	x.x	x.x	x.x	x.x	x.x	x.x	x.x	x.x	x.x	x.x	x.x	x.x	x.x
(Min, Max)	(x, x)	(x, x)	(x, x)	(x, x)	(x, x)	(x, x)	(x, x)	(x, x)	(x, x)	(x, x)	(x, x)	(x, x)	(x, x)

¹ Times are relative to time of dosing.

² Number of data points used to compute the summary statistics. For calculation of summary statistics, BQL values were imputed as 0 if they did not come after a PK sample concentration that is above the LLOQ and treated as missing otherwise.

PK Table 3: Summary Statistics for PK Parameters

[figure not shown]
Statistic	C_{max} (ng/mL)	T_{max} (h)	T_{last} (h)	$AUC_{(0-last)}$ (h×ng/mL)	$AUC_{(0-∞)}$ (h×ng/mL)	K_e (1/h)	$t_{1/2}$ (h)	CL/F (L/h)	V_z/F (L)
N									
Mean									
SD									
Min									
Median									
Max									
CV %									
GM									
GSD									

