6. GENERAL STATISTICAL CONSIDERATIONS

6.1. General Principles

Tabulations will be used extensively to summarize the data. Summary statistics for continuous data will include the mean, median, standard deviation, and range (minimum and maximum values). Summary statistics for discrete data will include counts and percentages, contingency tables, and associated confidence intervals (CIs). Denominators will be shown for all percentages (as N=X). When 95% CIs are given for a binary variable, Wilson Score CIs will be used. Parameters will be summarized overall and not by any subgroup.

In general, all data will be listed, sorted by subject ID, and when appropriate, by visit number within subject. The total population size relevant to specific tables or to columns or rows within tables will be displayed.

Listings of individual subject data include a Subject ID column. The subject identifiers assigned by site staff are replaced throughout this report with the SDTM variable USUBJID to protect the confidentiality of those who volunteered to participate in this protocol. USUBJID has been created as a composite of the 3-letter Electronic Data Capture (EDC) platform code followed by a numeric identifier assigned chronologically to enrolled subjects as well as screening failures across all sites and protocols in the EDC platform. Any data sharing activities will include the USUBJID and not the subject identifiers assigned at the site.

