6.5. Missing Data

All attempts will be made to collect all data per protocol. Clinical labs will not be collected for Day -1 if collected ≤ 7 days of dosing. Therefore, missing clinical laboratory results on Day -1 only will be imputed using last observation carried forward when results with 7 days prior to dosing are available. Missing clinical laboratory results on Day 4 or "Day 4 or ET" will not be imputed. Missing pre-dose PK samples will have concentrations imputed as BQL (below quantification limit). No other imputation will be performed for missing values. Outliers will not be excluded from the primary analyses. Outliers identified during the PK analysis will be discussed in the analysis report.

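### Late concentration summaries read too high wherever some but not all subjects are BQL, because BQL values after the first quantifiable sample are dropped

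*SAP*

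**What the plan says.** PK SAP 3.1 separates two kinds of BQL value. Those before a subject's first quantifiable concentration are set to 0 in the linear plots and in all calculations. For the rest, "All other BQL values will be treated as missing for all analyses". Footnote 2 to the PK Table 2 shell carries the rule into the concentration summaries: BQL values are "imputed as 0 if they did not come after a PK sample concentration that is above the LLOQ and treated as missing otherwise". The same footnote defines N as "Number of data points used to compute the summary statistics".

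Section 3.1 has one safeguard, for the GM only. A GM of concentrations "will be treated as missing for sets of data points containing an imputed 0 value due to a BQL value".

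PK Table 2 reports N, mean, SD, GM, minimum and maximum by nominal time, out to 72 h. It has no median row. Protocol 11.4 states "Summaries for continuous data will include minimum, median, mean, standard deviation, and maximum", and SAP 6.1 also lists the median for continuous data. The PK SAP Preface puts mean PK plots and concentration summaries in the CSR as a minimum.

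**The concern.** A BQL result is not unknown. It says that the concentration was below the LLOQ. Treating it as missing is reasonable when one subject's profile is analysed by NCA. In a summary across subjects at one time point, it removes the lowest values and leaves the rest to stand for the group.

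The two ends of the profile are also summarised on different bases. BQL values at the start count as 0 and suppress the GM. BQL values later produce no 0, so the suppression rule never acts and the GM is reported from the remaining subjects. A smaller N does not tell the reader why it fell, because missed samples and samples more than 10 min outside their window lower it too.

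At stake is how the late part of the concentration curve reads in the CSR. It could look higher or flatter than the data support.

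**Working it through.** **No figure to reproduce.** The plan gives no number on this point. The documents state no LLOQ and no between-subject CV, and the half-life is redacted. Direction can be settled without assumptions; size cannot.

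**Direction.** At one time point every dropped value is below the LLOQ and every kept value is at or above it. If at least one value is dropped and one kept, the mean, GM and minimum of the kept values must exceed those of the full set. The maximum does not change.

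**Worked example** (assumed values, LLOQ = 1, n = 8): 0.4, 0.6, 0.8, 1.1, 1.4, 1.8, 2.3, 3.0, so 3 of 8 are BQL.
- All values: mean 11.4/8 = 1.425, GM 1.18, minimum 0.4, median (1.1 + 1.4)/2 = 1.25.
- Plan's rule: N = 5, mean 9.6/5 = 1.92 (+35%), GM 1.80 (+53%), minimum 1.1.
- Each BQL value set as high as the LLOQ: mean (3 + 9.6)/8 = 1.575, still below 1.92.
- Median with BQL ranked lowest: 1.25, the same as with all values known.

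**Size.** Assume lognormal concentrations and a share p of subjects BQL. Let s = √ln(1 + CV²) and a = Φ⁻¹(p). Relative to all subjects, the plan's rule gives
- mean ratio = Φ(s − a)/(1 − p)
- GM ratio = exp[s·φ(a)/(1 − p)]

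For CV 50% and p = 0.25, s = 0.472 and a = −0.674. The mean ratio is 0.8743/0.75 = 1.166 and the GM ratio is exp(0.4724 × 0.3178/0.75) = 1.222. The full set:

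| CV | Mean ratio at 12.5 / 25 / 37.5% BQL | GM ratio at 12.5 / 25 / 37.5% BQL |
|---|---|---|
| 20% | 1.041 / 1.078 / 1.116 | 1.048 / 1.088 / 1.128 |
| 30% | 1.058 / 1.111 / 1.168 | 1.072 / 1.132 / 1.195 |
| 50% | 1.083 / 1.166 / 1.257 | 1.118 / 1.222 / 1.332 |
| 100% | 1.116 / 1.245 / 1.400 | 1.216 / 1.423 / 1.657 |

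The shares correspond to 1, 2 and 3 of 8 subjects. Simulation that drops the lowest 1 of 8 gives a similar answer at CV 50 to 100%: mean +7 to +11%, GM +10 to +18%.

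**Would LLOQ/2 repair the mean?** The mean ratio becomes Φ(s − a) + (p/2)·exp(s·a − s²/2). At 12.5 / 25 / 37.5% BQL this is 0.960 / 0.916 / 0.870 for CV 20%, 0.968 / 0.932 / 0.893 for CV 30% and 0.993 / 0.985 / 0.977 for CV 100%. In simulation at the same shares (7 or 8 subjects, trials with 1 to 3 BQL, median ratio to the full-sample SD), the LLOQ/2 SD is 50 to 77% too high at CV 20% and 25 to 40% too high at CV 30%. The plan's rule makes it 16 to 27% and 13 to 23% too low. Substitution helps the mean when CV is large. At CV 20% it only reverses the sign of the error in the mean, and it distorts the SD more than the plan's rule does.

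**The case against.** The strongest reply is that the problem may never arise and is already disclosed. Without an LLOQ or a half-life, nobody can say from the documents whether any sample to 72 h will be BQL. If one is, PK Table 2 prints every subject's value above the statistics and its footnote states the rule. PK Listing 4 shows reported and analysed values side by side, and PK Figures 1 and 2 show each profile. With seven or eight subjects, a careful reader can see what was dropped. The summaries are descriptive and no comparison is made.

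Most of this stands, and it keeps the point minor. But disclosure does not correct the statistic, and the mean and GM curves carry no individual values. Uncertainty about occurrence is a reason to settle the rule before the data are seen.

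The missing median row is a gap in the table shell whether or not any value is BQL. It is no evidence of bias, but it fits the same repair.

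A reader might infer that the primary PK results are biased, or that the choice of the 4-g dose for the thorough QTc study is at risk. The documents support neither. The NCA parameters come from individual profiles, AUC(0-last) ends at the last measured concentration, and nothing in the plan bases the dose decision on late mean concentrations.

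**Conclusion.** The concern holds in a limited form. The direction of the error is certain wherever some but not all subjects are BQL after the first quantifiable sample. Under the lognormal assumption with CV 20 to 100%, the mean is too high by 4 to 12% at 12.5% BQL, 8 to 25% at 25% and 12 to 40% at 37.5%. The GM is too high by 5 to 22%, 9 to 42% and 13 to 66%. The reported minimum cannot fall below the LLOQ. If no such sample is BQL, the effect is zero.

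The effect is confined to late descriptive cells of PK Table 2 and the late part of PK Figures 3 and 4. Severity is minor.

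**What to change.** In PK SAP 3.1, keep the missing-value rule for NCA only. In PK Table 2, for any BQL value after the first quantifiable sample, whether trailing or between quantifiable values:

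1. Add a row with the number BQL at each nominal time, separate from missed samples and excluded out-of-window samples.
2. Show the minimum as BQL when any value is BQL.
3. Add a median row with BQL ranked lowest, shown as BQL if a middle value is BQL. With 7 or 8 subjects, up to 3 BQL leave it unchanged.

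Amend footnote 2 to match, and mark on PK Figures 3 and 4 the time points where the plotted mean or GM omits BQL values.

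None of this imputes a value. The cost is two rows, an amended footnote, a few words in 3.1 and a figure note.

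Using LLOQ/2 in the mean and SD, or blanking the GM, should be options only. At CV 20 to 30%, LLOQ/2 makes the mean 3 to 13% too low and the SD 25 to 77% too high. It would also have to be squared with SAP 6.5, which says "No other imputation will be performed for missing values". Blanking the GM for one BQL subject discards a late point with 6 or 7 quantifiable values. Before either is applied to PK Figure 3, reconcile PK SAP 3.3, which says "GM plots of zoliflodacin PK profiles will be shown in PK Figure 3", with the figure shell, which is titled as a mean and has error bars of ±1 SD.

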3.2. Demographic and Baseline Characteristics

Sex, race, age, weight, height, and body mass index (BMI) of subjects in the PK analysis population will be listed and summarized (PK Table 1, PK Listing 1).

3.3. Dosing and Pharmacokinetic Sampling Summary

Subject dose administration times will be presented (PK Listing 2). Cases that potentially affect the analysis will be discussed.

Protocol deviations related to dosing or PK sampling will be listed (PK Listing 3) and summarized in the PK Report text. Deviations to be included in the PK Report include:

- Treatment administration deviations
- Blood specimen not collected
- Plasma specimen result not obtained
- Specimen temperature excursion
- Required specimen collected out of window
- Subject vomiting within 24 h of dose

- Subject ingestion of prohibited food or within the prohibited window after dosing
- Any other deviation determined by the PK analyst to be potentially affect PK

Drug plasma concentrations will be listed by subject (PK Listing 4), with nominal and actual time associated with the sample indicated (nominal time is defined as the time in h since the start time of the dose). Both laboratory reported concentration values, and modified concentration values used for analysis (for instance, imputation of 0 for a BQL value at baseline) will be included, as separate columns, in the listing.

Plasma drug concentrations will also be summarized (PK Table 2) and plotted. PK Figure 1 and PK Figure 2 will plot all individual subject plasma PK profiles, as linear and semi-logarithmic plots, respectively. Subject ID for each individual profile in these figures will be shown in a legend. GM plots of zoliflodacin PK profiles will be shown in PK Figure 3. Semi-log mean plots of zoliflodacin PK profiles will be shown in PK Figure 4.

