1. PREFACE

DMID protocol 16-0118 is a Phase 1 study of zoliflodacin in healthy male and female subjects. The pharmacokinetics (PK)-related objectives of the study are:

- To evaluate the plasma PK of zoliflodacin after administration of a single 4 g oral dose under fasting conditions

This document reiterates key PK elements in the study design of DMID Protocol 16-0118 and thoroughly describes the presentations and summaries of PK data as well as the noncompartmental analysis (NCA) to be included in the PK Report and summarized in the clinical study report (CSR) for this protocol. Shells and mockups are given for all PK-related tables, figures, and listings planned for inclusion in the CSR and/or PK Report. At minimum, mean PK plots as well as listings and summaries of zoliflodacin concentrations and PK parameters will be included in the CSR, while all tables, figures, and listings described in this document will be included in the PK Report.

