3.5. Descriptive Statistics

Subject-specific PK parameter estimates will be listed (Listing 5). PK estimates will be summarized in [PK Table 3](#). Summary statistics will include mean, standard deviation (SD), minimum, maximum, median, coefficient of variation as a percent (CV%), GM, and geometric standard deviation (GSD).

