APPENDIX 2. LIST OF PROPOSED PK FIGURES

[figure not shown]
LIST OF PK FIGURES

PK Figure 1: Concentration Profiles for All Subjects by Time	15
PK Figure 2: Semi-log Concentration Profiles for All Subjects by Time.....	16
PK Figure 3: Mean Concentration by Nominal Time	17
PK Figure 4: Mean Concentration by Nominal Time (Semi-Log)	18

[figure not shown]
PK Figure 1: Concentration Profiles for All Subjects by Time

PK Figure 2: Semi-log Concentration Profiles for All Subjects by Time

[figure not shown]

PK Figure 3: Mean Concentration by Nominal Time

Note: Error bars give ± 1 standard deviation.

PK Figure 4: Mean Concentration by Nominal Time (Semi-Log)

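### Does PK Figure 3, a geometric-mean plot in the PK SAP text but a mean ± SD plot in its shell, need a change to the plan?

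*SAP*

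**What the plan says.** Three statements in the PK SAP describe PK Figure 3.

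- Section 3.3 (Dosing and Pharmacokinetic Sampling Summary): "GM plots of zoliflodacin PK profiles will be shown in PK Figure 3". The next sentence reads "Semi-log mean plots of zoliflodacin PK profiles will be shown in PK Figure 4".
- Appendix 2, both in the list of figures and above the shell: "PK Figure 3: Mean Concentration by Nominal Time". The PK Figure 4 title is the same with a semi-log suffix.
- Appendix 2, below the Figure 3 title: "Error bars give ± 1 standard deviation".

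Section 3.5 and PK Table 3 list mean, SD, GM and GSD as separate statistics for the PK parameters. PK Table 2, which summarises concentrations by nominal time, has rows for N, mean, SD, GM and range, but none for GSD.

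Section 3.1 sets the handling of values below the quantification limit. Those before the first quantifiable value "will be imputed as 0 for linear plots and for all calculations including NCA and summary statistics", and a GM "will be treated as missing for sets of data points containing an imputed 0 value due to a BQL value". The Preface requires for the CSR: "At minimum, mean PK plots as well as listings and summaries of zoliflodacin concentrations", together with the PK parameters.

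**The concern.** A programmer has two instructions for one figure. The text asks for a geometric mean and gives no bars. The shell asks for a mean with SD bars. Because the plan keeps GM and mean apart elsewhere, the shell's title cannot simply be taken as shorthand for GM. Someone who tried to honour both would draw GM ± SD, an additive spread around a multiplicative centre. With skewed concentrations its lower bar sits too low and can fall below zero. The two readings also differ at time 0: the arithmetic mean plots as 0, whereas the GM is missing if pre-dose values are below the quantification limit.

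Plasma PK is the primary objective and mean plots are among the minimum CSR contents. It therefore looks as if the plan leaves open which centre and spread a prominent display will show.

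**Working it through.** **Which reading the documents support.**

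1. The shell is complete: a centre called mean with SD as its spread is the usual arithmetic pair. The GM reading in 3.3 has no matching spread.
2. PK Table 2 supplies what the shell needs (mean and SD at each time). It does not supply what bars around a GM would need, since no GSD by time point is planned.
3. The Figure 3 and Figure 4 titles differ only in the scale, as do those of Figures 1 and 2. That suggests one summary curve shown on linear and semi-log axes.
4. The summary plot is called a mean plot or mean profile in Protocol 11.4.4, PK SAP sections 1 and 3.1, and main SAP section 10. Only the one sentence in 3.3 calls it a GM plot.

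**How far apart the readings could be.** The plan states no figure to reproduce and gives no concentration CV. The CVs below are assumptions, with lognormal concentrations and GM set to 1:

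- arithmetic mean AM = √(1 + CV²)
- SD = CV × AM
- GSD = exp(√ln(1 + CV²))

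| Assumed CV | AM | SD | AM ± SD | GM ± SD | GM/GSD to GM × GSD |
|---|---|---|---|---|---|
| 20% | 1.020 | 0.204 | 0.816 to 1.224 | 0.796 to 1.204 | 0.820 to 1.219 |
| 30% | 1.044 | 0.313 | 0.731 to 1.357 | 0.687 to 1.313 | 0.746 to 1.341 |
| 50% | 1.118 | 0.559 | 0.559 to 1.677 | 0.441 to 1.559 | 0.624 to 1.604 |
| 100% | 1.414 | 1.414 | 0.000 to 2.828 | −0.414 to 2.414 | 0.435 to 2.299 |

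- *Centre:* the AM exceeds the GM by 2%, 4%, 12% and 41%.
- *Lower bar of the mixed version against GM/GSD:* at CV 30%, 0.687/0.746 = 0.92, so 8% too low; at CV 50%, 0.441/0.624 = 0.71, so 29% too low.
- *Upper bars:* they nearly agree at moderate CV (1.313 against 1.341 at 30%; 1.559 against 1.604 at 50%).
- *Negative lower bar:* GM − SD reaches zero when CV × √(1 + CV²) = 1, so CV² = (√5 − 1)/2 = 0.618 and CV = 0.786. Below about 79% the mixed bar stays positive in expectation.

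The GM ± SD column is prescribed by no single statement. It arises only if two conflicting ones are combined.

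**Time 0.** Section 3.1 already decides both cases. On the linear plot the arithmetic mean of leading imputed zeros is 0. A GM for such a set is missing, so no point is drawn. The analyst has a rule either way.

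**The case for a change.** The strongest case for acting is that the contradiction is explicit and the correction cheap. The adjacent sentences in 3.3 use GM for Figure 3 and mean for Figure 4, which could be a deliberate distinction. The wording elsewhere favours the arithmetic mean but does not prove it. Two competent programmers could produce different curves for a display that must appear in the CSR, and a reader could not say which one was pre-specified.

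The mismatch stands, and so does the point that the intended statistic is inferred. The consequence is small. The Preface sends the concentration summaries to the CSR with the plots, and PK Table 2 gives both centres and the SD at every nominal time, so the plotted centre can be read off against the table. A deliberate GM for Figure 3 would also leave the shell's title and its SD note out of step, whereas the arithmetic reading requires only one stray word. That Figure 4 does not name its mean is a matter of clarity, not a second conflict.

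One limit applies to all of this: the shell graphics are not reproduced, so axis labels could not be checked. If the bar note belonged to Figure 4, the mixed GM ± SD case would lose its basis, although the difference in naming would remain.

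**Conclusion.** This is a clerical slip in the labelling of one descriptive figure, and it does not call for a change to the plan. The sensible reading is arithmetic mean with SD bars, as the shell says and as the Protocol and both analysis plans otherwise describe the plot.

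Under the assumed lognormal CVs of 30% to 50%, choosing the other centre would move the plotted line by 4% to 12%. The worst mixture of the two instructions would lower the bottom bar by 8% to 29%. Larger distortions need CVs that the documents neither give nor suggest.

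The noncompartmental parameters, PK Tables 2 and 3, the listings and the individual profiles are the same under every reading. Protocol 11.1 sets no formal hypothesis, so no test or decision rests on the figure. Settling the label would tidy the document without altering any result.
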